4.2 Pseudonymised data content

At the end of the pseudonymised data collection phase, we will have drawn from 4 main sources for each participant:

- a. Pseudonymised data drawn from wearables, sensors, devices and monitors
- b. Pseudonymised related data drawn from several NHS sources
- c. Geographically related data drawn from environmental sources (MetOffice, DEFRA)
- d. Pseudonymised participant (with multiple morbidities) related questionnaire results including participant outcome measures

Pseudonymised data drawn from wearables, sensors, devices and monitors – individual participant specific (anonymised) data which will include: See table B above.

a. Pseudonymised patient data drawn from NHS including:

- GP or HCP attendances (or visits) in the period of study and would include reason for attendance
- NHS Hospital Episode Statistics (HES) data for South Lincolnshire, containing details of all
 admissions, outpatient diagnoses and A & E attendances, together with GP data records
 for the whole patient group for the 2 years preceding the study together with the study
 period and one year into the future to evaluate impact.
- Known procedures (OPCS, SNOMED CT, etc.)
- Prescribed drugs and changes in the period of the study (and make this for 2 year preceding the study and one year into the future).
- GP Data and Social Prescribing Data.
- Post code or postcode sector of patients to facilitate linkage to the deprivation index (IMD) and environmental data.
- Death or other severe events

19

b. Data drawn from environmental sources will include:

- Air quality and weather pollutant levels e.g. temperature, dew point, etc.
- Postal sector of pseudonymised patients
- c. QuestLink questionnaires at intervals including:
 - HowRu and Health Confidence Score (HCS) Person Reported Measures of Outcomes
 - Questions about events in the family
 - Medication related questions including use of "over the counter medications"
 - Activity levels

4.3 Clinical Event Grouping

To anticipate an illness is a clinical challenge. In many instances a future illness bears no relationship to the conditions the patient already has. There is evidence that patients presenting with a heart attack actually visited their GP with non-specific symptoms in the days prior to the onset of the heart attack symptoms. We aim to explore whether the likely "unplanned events" which are clinically orientated, that will "trigger further investigation and/or treatment" can be categorised; and subsequently explore whether the actual clinical event might have been prevented by acting on the "data signals"; these might arise from changes in the patient's behaviour, their physiology or their behaviour, or from the environmental or social determinants of health data. Table C below classifies the "type of clinical event" in the left column; the process that might have caused it in the middle column; and the clinical diagnosis that might be made in the right column. There will be a lot of overlap between the columns, but it may help relate different forms of classification to one another – the physiological and behavioural; the clinical; and the environmental and the social determinants of health.

Clinical Event (& Timing)	Туре	Reasons for illness	
Outpatient visit	New or Old (Follow-up)	What conditions?	
Acute In-patient stay (days)	Acute/Hospice/Palliative/Mental health/	Day ward assessment	
		Ambulatory ward assessment	
Infections	Upper and lower respiratory/chest/asthma/COPD /Gut/Sepsis/Flu/pneumonia/ENT	Respiratory/Sepsis/Infection/Malignancy	
	/Cellulitis/Covid-19		
Cardiovascular system	Heart attack/AF or PAF/Venous thrombosis/Stroke/TIA/Palpitation/Heart failure/Angina	Heart failure/ heart attack/rhythm	
Psychological events	Stress/dementia/confusion/Sleep issues/Smoking and drug habits/Activity levels/recent bereavement/Acute crisis	Alcohol, confusion, neuropathy/Mental	
Falls or unsteadiness	Trip/Fracture/head injury/Off legs	Musculoskeletal/ Frailty	
Social deprivation related	Multimorbidity cluster/new composite Health Index		
	Air quality and weather related respiratory exacerbation		

20

IRAS ID: 286225 CPMS: 44344 01/08/2020 [Proof of Concept – Smart Technology – South Lincolnshire]

PoC Protocol Version: 1.4

	Captures many social determinants of the population's health (postal code in UK; income category etc etc)

Table C - High Level Attempt to Classify Clinical Event with Type of Event and Possible Reason

5. Data flows and management

Our Digital Platform is a cloud-based platform purpose-built for healthcare utilising leading technologies and practices in security and privacy. Our proposed concept solution is based on collecting participant data using sensor based wearables, software based sensors using the camera on a smart phone or iPad and web-based questionnaires. This data is then ingested and stored, together with NHS activity data.

Data scientists and researchers will be able to perform their data analysis and model development using the cloud based platforms Workbench. This provides a collaborative development environment with tools like RStudio or Jupyter Notebooks using technologies like TensorFlow or PyTorch and visualisation tools like Tableau or MS BI Studio and manages the end-to-end process of analytics, analytics asset creation, deployment and support.

The cloud based platform is certified for ISO27001 (information security management system) and ISO27018 (protection of personally identifiable information (PII) in public clouds acting as PII processors). ISO27018 certification is a means to demonstrate EU GDPR compliance.

For the PoC, our commercial partner, Philips commits to:

- act as the Data Processor as defined in the EU General Data Protection Regulation (GDPR) and only process data as agreed with the Authority.
- use the relevant information standards as published by the Department of Health or NHS England for data collection, transfer, storage, processing & destruction throughout the PoC
- comply with Code of Practice on Confidential Information for data collection, transfer, storage, processing & destruction throughout the PoC
- leverage our extensive experience in interoperability, we will transmit and persist data using open interoperability standards where possible.
- use our global experience as a manufacturer of medical devices, certification to ISO13485 to
 ensure safe data collection, transfer, storage, processing & Logging service: provides
 centralised log management for collecting, analysing and displaying logs for cloud-native
 applications to analyse performance or bugs.
- providing Identity and Access Management (IAM); this is a secure, centralised mechanism to manage identities, authentication and authorisation of users, service and devices and enable access control. It includes Terms and Conditions Management to manage consent and ensure data security and privacy.

21

Our proposed solution is based on collecting participant data in an easy to use and scalable way through sensor based wearables, software based sensors using the camera on a smart phone or iPad and web-based questionnaires. This data is then ingested and stored, together with NHS activity data, into the Philips HealthSuite digital platform (HSDP), a cloud-based platform purpose-built for healthcare utilising leading technologies and practices in security and privacy. Data scientist and researchers will be able to perform their data analysis and model development within the HSDP using the HealthSuite Insights Workbench. This provides a collaborative development environment with tools like Studie. Buyeter Nethobers tools like RStudio, Jupyter Notebooks and TensorFlow and manages the end-to-end process of analytics asset creation, deployment and support.

Table D: DATA FLOWS

22

IRAS ID: 286225 CPMS: 44344 01/08/2020

[Proof of Concept – Smart Technology – South Lincolnshire] PoC Protocol Version: 1.4

Data Tables for Consent, Device Distribution and Research

Table E - Data flows and Data table for Content, Device Distribution and Research

5.1 Data Collection

5.1.1 Application of the i5 Diagnostic Stratification system

Helicon and its partner i5 Health will be applying the i5 Diagnostic Stratification system (i5 DST) – which uses algorithms based on Machine Learning, Neural Networks and Artificial Intelligence (AI) to analyse millions of clinical patterns from medical records to identify the most suitable cohort for this programme. More specifically, i5 DST is an algorithm-based Artificial Intelligence clinical evaluation tool that can identify undiagnosed patients with a high likelihood of having an undiagnosed Long Term Condition (LTC). It uses pseudonymised patient medical history and estimates the probability of the patient having or developing, an LTC. DST facilitates proactive patient management that delivers patient-centric care to reduce unscheduled admissions by targeting two groups of patients i.e. those with:

- High Probability of currently having an undiagnosed LTC
- Potential of developing an LTC in the near future

5.1.2 Testing prior to commencement of Proof of Concept Study

In the weeks preceding the commencement of the study the following will be performed on healthy consented volunteers and checked for:

- Data flows and quality from person to sensor/app/wearables and then to data store
- Identification of databases with air quality sensors and temperature measurements
- Data flow to check with expected normal measure and also with unexpected measure to facilitate the appropriate responses of their devices to detect an "event"

5.1.3 The start of the PoC Study

23

IRAS ID: 286225	[Proof of Concept – Smart Technology – South Lincolnshire]
CPMS: 44344	PoC Protocol Version: 1.4
01/08/2020	

The start of the PoC study will, in the first 2-3 weeks, entail the recording physiological and behavioural data on pseudonymised participants and will serve to calibrate the expected measurements of each individual participant. Once the formal cohorts have been created and the individuals are supplied with and using the appropriate equipment, data scientists from Helicon and i5 Health will use the unique research platform with six months of sensor based data. During data analysis and model development, various hypotheses will be tested against the data.

The use of QuestLink, an electronic questionnaire will enable us to collect mental, social and physical health status and its progression on individual participants on a regular basis. It can also serve as a messaging service to collect such information from the participants as a list of their current medication, wellbeing or their minor illnesses. It will enable the use of measures, relevant to patients with multimorbidity, of patient self-confidence (HCS) and Health Status (howRU).

5.2 Data analysis

The use of Artificial Intelligence (AI) is being increasingly used as predictive healthcare solutions to provide early detection of long term conditions that anticipate and can thereby prevent illness and disease. One such common example of this technology used for screening is Atrial Fibrillation (AF) which utilises Artificial Intelligence techniques such as Principal Component Analysis (PCA) and Neural Networks (NN) (Ref Braun 2018). Artificial Neural Networks (ANNs) provide a powerful technique for modelling complex non-linear relationships for classification. Neural Networks are commonly applied in non-linear predictions to analyse the complex relationships and correlation that exist between patient history including the social determinants of health, and development of future conditions, and also between the physiological and behavioural measurements.

The NHS has the great advantage of having vast amounts of historic patient data in standardized form suitable for analysis and AI training. The Healthcare industry is data-rich, but it is not always possible to extract the required information from the data in a timely manner or in a manner that is useful to the patient or healthcare professional.

As a separate part of the study (phase 2) we intend to make assessments of the likely qualitative and economic benefits of the predictive system based on the data collected. These will be tested through data quality evaluation, model selection, training data categorisation, leaning algorithm(s), sensitivity and specificity analyses to help determine the confidence of the predictive systems (Ref: Longstaff 2010). The benefits can accrue in several parts of the "services". We will attempt to define the proportions in each.

Benefits will accrue to the patient, the family and work; they will also accrue to the health and social services when the specific event or illness is avoided. We will study trends across the cohort that were part of the PoC (patient participation groups PPG) compared with a similar cohort of patients that were not part of the PoC (patients reference group PRG) and report on the findings.

The design of the input data set requires the size of the data set to be defined. A larger data set will require more time to train the machine learning algorithms. The balance between learning capability and learning time will be considered and set with outcome requirements. The methodologies for the clinical components are based on existing implementations of Neural Networks for preliminary diagnosis to support targeted screening in the NHS.

Developing of machine learning algorithms can be split broadly into five stages.

24

- a) Obtain data that is pseudonymised and consists of a representative cross-section of patients with and without the condition or an adverse event
- b) Reduce the number of feature parameters that are relevant using de-correlation methods such as Primary Component Analysis (PCA)
- c) Split the data for machine learning training, monitoring of overfitting and performance testing to facilitate evaluation of prediction quality and applicability
- d) Train various machine learning models and topologies to evaluate which combination works best for the required predictions
- e) At the end of the study, device data will be connected to primary and secondary care data to build full medical records of participating patients. Such longitudinal medical records facilitate the prediction of future events to deliver pro-active care.

Joining the Device Data with GP and Hospital data requires a consistent key across all three data sets. Depending on the data structures held at Arden and Gem (AGEM) CSU, the Trial IDs can be mapped to a clear either to clear or pseudonymised NHS number, with a preference for pseudonymised NHS numbers.

GP and Hospital data extraction will be performed by applying the list of participating patients as a filter. This filter will be the list of pseudonymised NHS number where possible. The resulting data structure will be a collection of clinical and non-clinical data sets that can be linked via a pseudonymised primary key, or NHS number, location and calendar date for air pollution or weather data. **See table E – above**

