2.1 Testing the hypothesis

The principal research question is to test the hypothesis:

"If information about patient behaviour, conditions and events, captured from wearables and other smart technologies can predict demand for services, then providing these technologies to patients and using the data generated, will enable providers to pre-empt and redirect demand or design new services."

9

The hypothesis will be tested by deploying smart technologies with sensor-based wearables, software sensors using the camera on a smart phone or tablet, and web based questionnaires to study data from the participants.

We will further include pseudonymised Health and Social Care and Environmental data and store it together in a cloud-based platform purpose-built for healthcare, utilising leading technologies and practices in security and privacy.

Data scientists and researchers will perform data analysis and model development within the collaborative development environment with tools that manage the end-to-end process of analytics, analytics asset creation, deployment and support.

We will also be testing whether the use of multiple smart technologies of this nature, is acceptable to patients, easy to use and comfortable.

The analytics will seek to understand whether the use of such technologies and the data gathered from them, can indeed provide useful information in predicting adverse healthcare events and therefore inform the transformation of health services to make interventions sooner to achieve better outcomes.

3. Study design

A high-level outline of the research study design is illustrated below in Table A.

Table A: High Level Outline of Research Design

Our research is observational only and based on historic data. No clinical interventions to a patient's usual care will be made during the study as a result of any data collected. All the data collected will be pseudonymised and will not be monitored or analysed in real time.

The participant will not be able to see the physiological health readings recorded by the smart technologies and so will not have new information about their health which might prompt them to contact their GP or other healthcare services. Therefore, the clinical care of the patient will continue as normal by their GP and/or other health care professionals. This will be fully explained to participants during the recruitment and consenting process.

10

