5.4 Study Steering Group

A Study Steering (SSG) will oversee the organisation, the data quality and the output of the study. The steering group will oversee the data flows and management. To aid them they will use make use

25

of a monitoring device that ensures the correct and consistent correlation of the participant's PoC study number with the ID number of the wearable, sensor and monitor; and will generate a warning of any inconsistency.

Table F below illustrates the flow of data in the analytic phases of the PoC Smart Technology DataStudy Trial:

Phase 1 with the flow from the physiological and behavioural data mainly but with QuestLink data also

- Phase 2 with the additional data from the clinical health and social care data, together with Air quality
- Predict events Phase 1 with the "predict events" data
- Budget Phase 1 with the budget data linked to the relevant phases and support the development of the transformation report

Commented [CP8]: Needs rewording to fit with new study stages Data Collection Analysis Results

6. Ethical Considerations

Due to Covid-19, consenting processes have been adapted to ensure that consent is undertaken remotely. We considered adopting electronic means but have now decided to adopt a modified paper based system which has produced good results and with which the LCRN are familiar.

The research team will provide GP Practices with the following "participant facing documents" to use in recruitment activities with their own patients:

1. Participant Invitation Letter

26

IRAS ID: 286225	[Proof of Concept – Smart Technology – South Lincolnshire]
CPMS: 44344	PoC Protocol Version: 1.4
01/08/2020	

This will give a brief summary of the study and instructions on how to either accept or decline the invitation.

2. Participant Information Sheet (PIS)

This will provide a more detailed explanation of the study including what the participant will need to do, why we are undertaking the study, how they can withdraw from participation etc. a copy of the PIS has been submitted with this application.

3. Study Consent Form

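### The planned analysis never shows what device data add to existing NHS records, so prediction that comes from the records could be credited to the devices

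*Protocol*

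**What the plan says.** Section 2.1 sets the question: whether the technologies and the data they yield "can indeed provide useful information in predicting adverse healthcare events".

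Section 5.2 names the accuracy measures, as part of a separate Phase 2 assessment of qualitative and economic benefit: "sensitivity and specificity analyses to help determine the confidence of the predictive systems". They stand in a list with data quality checks, model choice and learning algorithms. No threshold or target is given.

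The same section describes model development in five stages. Stage d is the only model comparison: "Train various machine learning models and topologies to evaluate which combination works best for the required predictions". Stage e does the linkage: "device data will be connected to primary and secondary care data to build full medical records of participating patients". It adds that the linked records make prediction of future events possible.

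Section 5.4 gives the order of the data: "Phase 1 with the flow from the physiological and behavioural data mainly but with QuestLink data also", then "Phase 2 with the additional data from the clinical health and social care data, together with Air quality".

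The material for a records-only model is already planned. Section 4.2 draws HES and GP records "for the whole patient group for the 2 years preceding the study together with the study" period and one further year.

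**The concern.** The question is about information from the devices. Records of past admissions, attendances and prescriptions may predict later events too, and the NHS holds them whether or not anyone wears a device. If accuracy is reported only for a device-led model and for a linked model, neither figure says whether the devices told the NHS anything it could not have worked out from its own records.

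The results are meant to inform service redesign and a benefit assessment. If the linked model's accuracy were read as evidence for the devices, services could be advised to buy and support technology for prediction that the records supply without it.

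**Working it through.** **1. The plan's own figures.** There is nothing to reproduce. Section 3.1 gives a target of 500 participants from at least 700 identified (500/700 = 71.4%), with no event rate, accuracy target or precision requirement.

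**2. What each planned comparison can show.**

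| Planned step | Place | What it shows |
|---|---|---|
| Mainly device and questionnaire data | 5.4, Phase 1 | Whether device data predict by themselves |
| Those data plus clinical, social care and air-quality data | 5.4, Phase 2 | What records add to devices |
| Different models and topologies | 5.2, stage d | Which algorithm does best |
| Participants against a similar cohort outside the study | 5.2 | Trends, not predictive accuracy |
| Records alone against records plus devices | nowhere | What devices add to records |

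Only the last row isolates the device contribution.

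**3. The linked model when devices add nothing.** All inputs are assumptions: a binormal model, specificity fixed at 80%, and records-only AUC from 0.65 to 0.80. With Φ the normal distribution function and z its inverse,

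sensitivity = Φ(√2 · z(AUC) − z(0.80)), where z(0.80) = 0.842.

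| Records-only AUC | √2 · z(AUC) | Sensitivity at 80% specificity |
|---|---|---|
| 0.65 | 0.545 | 38% |
| 0.70 | 0.742 | 46% |
| 0.75 | 0.954 | 55% |
| 0.80 | 1.190 | 64% |

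A logistic simulation (400,000 records, 20% events, device signal carrying no information beyond the records) gave the same sensitivity for records alone and for records plus device, to within 0.1 percentage point. The linked model looks predictive, and the benchmark shows a device increment of about zero.

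**4. The device-led model in the same simulation.** Let the device signal be correlated with the records score but unrelated to the outcome once that score is known.

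| Records-only AUC | Device-only AUC, correlation 0.5 | Device-only AUC, correlation 0.8 |
|---|---|---|
| 0.65 | 0.58 | 0.62 |
| 0.70 | 0.60 | 0.66 |
| 0.75 | 0.63 | 0.70 |
| 0.80 | 0.65 | 0.74 |

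A device-led Phase 1 model can therefore do moderately well with no increment at all.

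**5. Precision.** With 500 participants and an assumed 10% to 30% having an event, there are 50 to 150 events. An assumed 30% test set leaves 15 to 45. The 95% half-width for one sensitivity near 50% is 1.96 · √(0.25/n):

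- n = 15: 25 points
- n = 45: 15 points

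The paired difference between two models on the same people has a different standard error, but the number of events will limit it as well.

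**The case against.** - **No success rule is stated.** A reader might infer that the study's success is judged by sensitivity and specificity of the linked model. The documents do not support that. The measures sit in a list under the Phase 2 benefit assessment, and no sentence confines them to the linked model. What stands is that no other accuracy measure is named and no records-only comparison is described.
- **Phase 1 is device-led.** This is true, so device data are not seen only in combination. But working step 4 shows that a device-led result does not answer the question of added value.
- **Linkage is needed anyway to obtain outcomes.** Also true: section 4.2 takes attendances, admissions and deaths from NHS sources. Stage e nevertheless presents the linked record as a basis for prediction, not only as a source of outcomes.
- **The stratification tool as a ready benchmark.** Section 5.1.1 says of it: "It uses pseudonymised patient medical history and estimates the probability of the patient having or developing, an LTC". A reader might infer that records already supply the prediction at issue. They may, but this sentence does not show it. The tool concerns long-term conditions and is used to find the cohort, while section 4.3 concerns unplanned clinical events.
- **False alerts.** A reader might also infer that nearly all alerts would be false. That depends on an event rate the protocol does not give. With weekly prediction, 80% sensitivity and 90% specificity (all assumed), the predictive value is 4% to 9% at 0.3 to 0.6 events per person-year, but about 32% at 3 per person-year. Section 4.3 covers many kinds of event, and the study issues no real-time alerts.
- **A statistical analysis plan could add the comparison.** It could, and choices of metric and interval belong there. But the comparator for the principal question is a matter of design, and sections 5.2 and 5.4 set out the sequence without it.

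**Conclusion.** The point holds as a gap in the comparison. Followed as written, the analysis can show that a device-led model predicts and that a linked model predicts, but not that the devices add to what the NHS already holds.

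The illustrated size, 38% to 64% sensitivity at 80% specificity from uninformative devices, rests on assumed records-only AUCs and a binormal model. It shows how far the linked figure could mislead and does not forecast this study's results. The finding itself rests on the text and needs none of these numbers.

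This is a worthwhile and cheap improvement to an exploratory proof of concept. It does not show that the study will reach a wrong conclusion.

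**What to change.** In section 5.2, state two nested models, fitted on the same participants and assessed on the same held-out split:

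1. the two-year prior HES and GP history, demographics and residential setting;
2. the same, plus device and questionnaire data.

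Residential setting belongs in the first model because sections 3.4.1 and 4 expect care-home residents to have more events.

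Report the difference in held-out discrimination, and in sensitivity at a fixed specificity, with a bootstrap interval that resamples participants. Base statements about the value of the devices, including those in the Phase 2 benefit assessment, on that difference. The device-led Phase 1 model can stay as a description.

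Cost: one extra model on data already planned. The increment will be imprecise with about 500 participants, and the reported benefit of the devices may look smaller.

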- they will be informed that the PoC has been approved by the Health Research Authority, which includes Research Ethics Committee review;
- g) they will be informed of the outcomes of the PoC at the end of the study;
- h) they will be informed that their data being used in the PoC is pseudonymised and they cannot be identified.

Their own GP will not be able to see this pseudonymised data. We will NOT be using face-to-face methods because of precautions to Covid-19. Instead we will be using "participant facing documents" to use in recruitment activities, to explain the study and will be encouraging questions, with the intent of ensuring that they are fully informed in some detail.

From the moment the participant agrees to join the trial, and for the duration of the trial, the participants data will be pseudonymised; the participant will have understood this when they agree to consent.

7. Monitoring and auditing the study

The Chief Investigator (CI) will ensure there are adequate quality and number of monitoring activities conducted by the study team. This will include adherence to the protocol, procedures for consenting and ensuring adequate data quality.

The Chief Investigator will inform the Sponsor should concerns arise from monitoring activities, and/or if there are problems with oversight/monitoring procedures.

8. Training

The Chief Investigator/ Coordinator will review and provide assurances of the training and experience of all staff working on this study. Appropriate training records will be maintained in the study site files. A copy of these documents will also be kept at the Sponsor Site. Site inductions will be undertaken by the CI and coordinator in order to train local staff.

9. Assessment and Management of Risk

The following represents a table listing potential risks and mitigations:

Risks	Mitigation
Electrical risk	ActivInsights device is CE Marked and is approved by NHS for Research. Other devices are apps and non-wearable.

28

 IRAS ID: 286225
 [Proof of Concept - S

 CPMS: 44344
 PoC Prote

 01/08/2020
 PoC Prote

[Proof of Concept – Smart Technology – South Lincolnshire] PoC Protocol Version: 1.4 **Commented [CP9]:** Needs rewriting to remove the repeated information from recruitment section above and replace with: Considerations related to:

- Covid-19

- Covid-19
 Non-interventional collection of data and blinding of
- results to participants
- How care home staff will be asked to participate (refer to SOP)

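### The study can test whether the data predict demand, but not whether using them pre-empts or redirects it, and the participant versus non-participant comparison cannot fill that gap

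*Protocol*

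**What the plan says.** **The question.** Protocol 2.1 makes the full conditional statement the principal research question: if the captured information predicts demand, then providing the technologies and "using the data generated, will enable providers to pre-empt and redirect demand or design new services". Section 1.3 gives essentially the same hypothesis. Both sections say it will be tested by deploying the devices.

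**Use of the data.** Section 3 allows no clinical change to a patient's "usual care will be made during the study as a result of any data collected" and says the data are not monitored or analysed in real time. Section 1.3 also excludes participant-level intervention and blinds the readings to participants. Section 6 adds: "Their own GP will not be able to see this pseudonymised data".

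**Benefit and comparison.** Section 5.2 describes benefits to the patient, family and work, and continues: "they will also accrue to the health and social services when the specific event or illness is avoided". The next sentence reads: "We will study trends across the cohort that were part of the PoC (patient participation groups PPG) compared with a similar cohort" of people outside the study, the patients reference group (PRG). Section 4.2 collects hospital and GP records for the two preceding years, the study period and "one year into the future to evaluate impact". Sections 1.3 and 5.2 separately plan an assessment of likely qualitative and economic benefits in Phase 2, using model selection and sensitivity and specificity analyses.

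**The concern.** The second half of the hypothesis is about what happens when providers use the data. In this study no provider does. A statement that the whole hypothesis will be tested therefore promises a conclusion the design cannot deliver.

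The participant versus PRG comparison makes this more than loose wording. It is placed next to a sentence on avoided events, has no other stated purpose, and sits alongside a follow-up year described in terms of impact. If participants turned out to have fewer events, that result could easily be taken as support for the untested half. The programme is meant to lead to service recommendations and an economic assessment, so the distinction between predicting demand and reducing it affects what the NHS may conclude.

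**Working it through.** The protocol gives no event rate, effect size, significance level or power for this comparison, so there is no figure of its own to reproduce. The check is mainly one of logic.

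**Step 1. What each part of the hypothesis needs, and what the study supplies.**

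- *The data predict demand.* This needs device, questionnaire and environmental data linked to later health-service events in the same people. Sections 4.2 and 5.2 provide that. Testable.
- *Using the data lets providers pre-empt or redirect demand.* This needs some patients or services in which the data are used, and others in which they are not. Sections 1.3, 3 and 6 exclude use among participants, and the PRG has no device data to use. No contrast exists. Not testable.
- *Using the data lets providers design new services.* Phase 2 (1.3) develops use cases, pathways and service recommendations. Addressed descriptively, not tested.

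**Step 2. What a participant versus PRG difference would consist of.**

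Observed difference = effect of acting on the data + selection + monitoring reactivity + unequal data capture + chance.

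- *Effect of acting on the data:* zero during the study, by 1.3, 3 and 6.
- *Selection:* participants have capacity and are not on palliative care (3.1). They are screened by GP practices or care-home staff (3.2). Those living at home must opt in and are dropped after two weeks without a reply (3.3.1). How the PRG is made similar is not stated.
- *Reactivity:* reduced by blinding but not removed. Participants enter their own temperature six times a week (4.1), answer questionnaires about twice weekly (3.4.1) and have support contacts (3.4.3).
- *Data capture:* 5.2 extracts GP and hospital records using the list of participating patients as a filter, and gives no extraction route for the PRG.

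Adjustment or matching could shrink the selection term. It could not make the first term anything other than zero.

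**Step 3. Illustration only: how easily selection could look like a result.** Assumptions, none from the protocol except n = 500 participants: 500 PRG patients; PRG event risk p0 of 20% to 40%; participants' risk p1 lower by a relative 20% through selection alone; two-sided 5% test of levels, with p̄ the mean of p0 and p1.

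Probability of significance = Φ{[(p0 − p1) − 1.96 × √(2p̄(1 − p̄)/n)] / √([p0(1 − p0) + p1(1 − p1)]/n)}

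- p0 = 0.20, p1 = 0.16: (0.04 − 1.96 × 0.02430)/0.02427 = −0.31, probability 0.38.
- p0 = 0.40, p1 = 0.32: (0.08 − 1.96 × 0.03036)/0.03025 = 0.68, probability 0.75.

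The same calculation gives 0.12 to 0.26 for a 10% lower risk and 0.72 to 0.98 for a 30% lower risk. With 2,500 PRG patients the ranges for 10%, 20% and 30% are 0.17 to 0.39, 0.55 to 0.93 and 0.90 to 1.00. A larger reference group makes a false signal more likely, not less. These figures show a mechanism and do not estimate the bias in this study.

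**The case against.** **The protocol does not say that benefit will be concluded from participants versus PRG.** A reader might infer that it does, because the sentence on avoided events comes immediately before. But the text says only that trends will be studied, "compared with a similar cohort of patients that were not part of the PoC (patients reference group PRG) and report on the findings". It names no outcome, benefit estimate or decision rule. The stated route to benefit is the model-based Phase 2 assessment, whose word for the benefits is already likely. This objection stands. What remains is that the comparison has no stated purpose and its placement invites the wrong one.

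**The working aim is already close to prediction.** The last paragraph of 2.1 asks whether the data give useful information for predicting adverse events, and 4.3 speaks only of exploring whether an event might have been prevented. True, and it makes the fix easy. It does not remove the statement in 1.3 and 2.1 that the whole hypothesis will be tested.

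**The impact wording in 4.2 is ambiguous.** It does not say impact of what and is not tied to the PRG. The no-intervention statements in 1.3 and 3 are also limited to the study itself, so a nil effect in the following year is partly an inference. This stands as a limit. Still, the protocol describes no use of the predictions in these participants' care during that year.

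**Trends and two prior years of records help.** A fixed selection difference would be visible at baseline, so a naive comparison of levels is not what the protocol specifies. Comparator definition may also be left to an analysis plan. Both points stand against putting a size on the bias. Neither creates a contrast in use of the data.

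**Conclusion.** The point holds on the protocol's own text. As designed, the study can support a conclusion that the data predict demand. It cannot support a conclusion that using the data pre-empts or redirects demand, and participants versus PRG cannot supply that evidence.

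The size is categorical: during the study the effect of acting on the data is nil by design, so none of an observed difference could be attributed to it. This rests on the no-intervention, no real-time analysis and no GP access statements being followed. For the extra year it rests on the absence of any described use of the data.

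Three stronger readings are not supported:

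- That the protocol plans to read benefit from this comparison. Section 5.2 does not say so.
- That a number of falsely avoided admissions can be given. No admission rate or selection effect is in the document.
- That the whole hypothesis is untestable. The prediction half is testable within participants, and service design is covered descriptively.

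**What to change.** - **1.3 and 2.1:** limit the tested hypothesis to prediction of demand. State that pre-empting or redirecting demand is not tested, and that service design is addressed descriptively in Phase 2.
- **5.2:** state that participants versus PRG is descriptive, covering representativeness and reactivity to monitoring, and is not evidence of benefit.
- **4.2:** replace the impact purpose of the further year with follow-up of outcomes for prediction.
- **1.3 and 5.2, Phase 2:** label the benefits as modelled projections under an assumed range of preventable shares of predicted events.

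There is no need to require a matched PRG from the same search list. At the protocol's minimum of 700 identified and its target of 500 recruited, about 700 − 500 = 200 people would remain. Most would be people who did not consent, and their records would need an extraction route beyond the participant filter in 5.2.

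The cost is wording only; no prediction analysis is lost. The downside is a narrower conclusion.
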